### **TIME-TABLE OF PHASE 2:**

The chronology can be summarized as:

Months 6-8: Selection/confirmation of solutions, and methods for contact identification, diagnosis, treatment and reporting. Training, then introduction of solutions at the sites (as soon as each site is prepared). Continued outcome measurement at all sites.

Months 9-12: All intervention sites have started, and are 'scaling up' to fully implement all planned solutions.

Months 13-18: Full implementation of all solutions at all Intervention sites

Data analysis – we anticipate this will be finished quickly as it is very simple – involving simple counts of outcomes from the contact diagnosis and Contact treatment quarterly reports, with verification from the source documents – the Contact Registries

### **ETHICAL CONSIDERATIONS FOR PHASE 2:**

*Individual consent will not be sought for Phase 2.* The interventions themselves pose no risks to trial participants, and indeed represent best clinical practice. All procedures that directly impact patient care will be approved by health officials, and by the site staff themselves. These procedures will be implemented as part of routine practice – that we hope will continue long after the trial is completed. As part of that routine health care, the agreement of patients and their contacts will be necessary – particularly for things that patients may consider more intrusive such as providing information on their household contacts, or allowing home visits by site staff. However this should not require consent as it will be part of standard care and is not part of a direct research intervention.

An important ethical issue is that of withholding a potentially effective intervention in some sites while it is introduced in others. However, we will not withdraw any programs or practices that are part of current or standard practice at the sites. More importantly, there is equipoise, as we are not certain that this complex intervention (or the specific solutions) will work.

### **SECONDARY STUDY - CROSS OVER STUDY (PROVIDING THE INTERVENTION TO CONTROL SITES):**

**Objectives:**

- 1) To evaluate the sustained effect of this complex intervention for one year after the end of the randomized trial – at original intervention sites.
- 2) To evaluate the costs, and impact of a stream-lined Phase 1 and 2 – administered to control sites, after the 18 month trial.

**Design:**

In the cross-over study the intervention sites now become control sites, and the control sites now receive the intervention. In the cross-over study the entire intervention of evaluation, decision making and implementation of solutions (i.e. Phase 1, transition, and Phase 2) should take a total of 12 months. Hence all activities must be streamlined. Outcomes will be measured as before – monthly – at all sites.

*Phase 1:* Phase 1 is shortened to 3 months. During Phase 1, questionnaires are administered to health care workers, contacts, and index cases as in the main study. However, these questionnaires are much shorter - 10 to 15 items which are mostly open-ended questions. These questionnaires are also virtually identical to each other, facilitating analysis. In Brazil, we will assess whether these can be self-administered or must remain interviewer administered. This means the time taken to complete the questionnaires, and enter the data will be measured, as well as the information collected will be compared descriptively.

The cascade analysis is not changed. Data on all seven Cascade steps will be abstracted for approximately 100 identified contacts – meaning for about 30-50 index cases (depending on number of contacts identified per index case.) We will review consecutive index cases, with the last reviewed diagnosed 6 months earlier (meaning we go back in time from 6 months to 7, then 8 and then 9, etc, until the required number of contacts are available). This 6 months limit is imposed because it can take several months for identified contacts to be reached, screened, evaluated, and therapy proposed and refused/started.

For costs – labour costs for personnel will be estimated using the time and motion studies as in the main study. These will be streamlined in that most of the general questions are eliminated. Facility costs, and hourly wages will be collected using the health facility questionnaire – most sites will complete this while control sites (before the cross-over), but if this was not completed, this will be done in Phase 1 of the cross-over. In Phase 2 of the cross-over, all sites will complete a brief update of the health facility questionnaire – which will ascertain if there have major changes in the staffing and other costs related to the TB program at that facility if this has not been completed before at the participating sites (most sites will have done this).

*Transition:* There are 3 months between Phase 1 and Phase 2. The first month will be used for data analysis – which will be primarily descriptive. In the second month we will present the questionnaires and cascade analysis findings to the local TB program managers as well as clinic managers and discuss potential solutions. In the 3rd month we will prepare materials and supplies for Phase 2, and conduct all necessary training – for LTBI management, registry use and analysis.

*Phase 2:* Phase 2 will last 6 months. The (new) intervention sites will receive in-service visits weekly for the first month, then twice a month for months 2&3, then monthly for Months 4-6. All sites will now use the new registries; no further changes will be made to these registries, once the site specific registries were developed in the Main trial. Interim Cascade analysis will be done at end of Month 3 in the Cross-over

intervention clinics; these results will be shared with the staff and administration of these clinics, to identify remaining/unresolved problems, and generate new solutions to correct these problems.

Outcomes will be continued to be measured as before and will also continue to be measured in former intervention sites. Clinical TAMs will be measured twice at all sites Research. TAMs will be measured monthly as before.

### **Data Analysis:**

There are three main comparisons:

First, we will compare the results at the original intervention clinics, from the last 6 months of the Primary study with the last 6 months of the secondary study - to assess whether any benefits found are sustained over time.

Second, we will assess the increase in contacts seen, investigated, started and completing LTBI treatment at the former control sites by comparing these numbers in the last 6 months of the Primary study with the last 6 months of the Secondary study.

As before, our analysis will be performed at the level of the individual, but will account for correlation between subjects from the same centre. Population averaged logistic regression with an identity link estimated via generalized estimating equations (GEE) and using a jack-knife estimate of the variance will be used to assess the effect of the intervention on the primary and secondary outcomes above, depending on the type of outcome (e.g. count or proportion). This approach will account for the correlation between subjects in the same cluster, and for varying cluster sizes. Using an identity link (rather than a logit link) will allow us to estimate risk differences for binary outcomes.

Population averaged models estimated via GEE are robust to mis-specification of the correlation structure. While our data will surely have clustering at the household level as well, we need only account for the top-level cluster (here centre) and use the empirical standard errors to ensure that our inferences are conservative.

For count type outcomes, we will use a similar approach as described above, but using a Poisson distribution.

In secondary analyses, we will use logistic regression with a logit link estimated via GEE and also adjust for additional confounders (country, age, sex and smear status of index case). In sensitivity analyses we will analyze at the level of the cluster. Missing data will be dealt with via multiple imputation using chained equations which will allow us to impute binary as well as continuous variables.

Third, we will estimate the cost-effectiveness of the streamlined intervention given to the former control sites in the secondary study. This will be estimated as the total research and health system costs for the Phase 1 and Phase 2 intervention package per added contact who starts LTBI therapy. This can also be compared to the cost-effectiveness (estimated in the same way) of the original intervention given to the original intervention sites.

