### **Rationale for study design**

The study is designed as a pragmatic public health intervention study in that the intervention package will be tailored to the problems identified from the standardized public health evaluation in that country.

The specific problems and changes required will not be exactly the same in all sites, raising potential concerns over generalizability. **However the intervention being tested is the approach – a standardized public health evaluation and analysis, with identification of problems (barriers), and appropriate solutions.** The initial evaluation will utilize standardized questionnaires, and data gathering to facilitate replication in other settings. We have reduced the variability of the final solutions package by limiting the budget allocated for these solutions. This type of public health intervention has been used successfully in other cluster randomized trials - training hospital staff in Senegal and Mali to conduct maternal mortality review resulted in reduced maternal mortality, and facilitation of women's group meetings in Nepal lead to improved birth outcomes. In both studies the actual solutions that were implemented were site-specific; it was the process to identify problems that was standardized.

The choice of LTBI treatment regimen by the primary providers will follow local treatment guidelines. This for several reasons: i) The primary objective of the trial is to evaluate interventions up to treatment initiation – which will not be affected by the treatment selected; ii) The current standard in most countries remains INH for 6 or 9 months; iii) The 4RIF vs 9INH trial will only be finished in early 2017, so findings from that RCT will not affect practise until close to the end of this study.

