### **Estimation of costs, and cost-effectiveness:**

We will estimate the total Investigator, research staff, and clinic staff time involved in data gathering in Phase 1, and for training, implementation, supervision, and for each type of solution delivered to patients in Phase 2. This will be based on the time spent on different study related activities, recorded by research and clinic staff in their time logs. The total effort for public health evaluation and intervention implementation for health facility staff and research staff will be estimated from these total times. The average salaries of the different cadres of health facility workers will be used to value these activities. From this we will estimate total costs for each activity, and from the numbers of index cases and contacts derive an average cost per index case, or per contact. The primary cost-effectiveness measure will be the total cost of all Phase 2 activities *per additional contact who starts LTBI therapy*. Additional will be calculated based on the difference in proportion starting LTBI therapy between the pre- and post-intervention periods.

As well we will tabulate all diagnostic tests, visits and drugs related to contact management. Costs for these health care activities will be estimated using the WHO cost indices as described above. Patient costs will be ascertained in a sample of patients based upon a short interviewer-administered questionnaire regarding time taken for the various steps of the contact investigation and management as well as their out of pocket expenses related to travel, food etc. Incremental health system costs will be expressed per additional contact initiating LTBI (primary outcome), and per additional active TB case detected, and per contact completing LTBI therapy (secondary outcomes) as measures of cost-effectiveness.

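### The cross-over analysis judges the sustained and the streamlined effect by each group's own before-after change, so a common time trend enters both estimates

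*Protocol*

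**What the plan says.** The cross-over Design section states "In the cross-over study the intervention sites now become control sites, and the control sites now receive the intervention". Study design and the cross-over section keep outcome measurement going, monthly and at all sites, for 12 further months.

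The cross-over Data Analysis section then lists three main comparisons.

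- Sustained effect: "First, we will compare the results at the original intervention clinics, from the last 6 months of the Primary study" are compared "with the last 6 months of the secondary study - to assess whether any benefits found are sustained over time".
- Streamlined effect: former control sites are assessed by "comparing these numbers in the last 6 months of the Primary study with the last 6 months of the Secondary study".
- Cost-effectiveness of the streamlined package: "total research and health system costs for the Phase 1 and Phase 2 intervention package per added contact who starts LTBI therapy", with no comparator named. For the main study, the cost section fixes one: "Additional will be calculated based on the difference in proportion starting LTBI therapy between the pre- and post-intervention periods".

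The model is a GEE clustered on centre. The covariates listed for the secondary analyses are country, age, sex and smear status of the index case. No between-group contrast and no term for calendar time or group by period is stated.

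**The concern.** Secondary objectives 3 and 4 ask whether the effect lasts for a year and what the streamlined version achieves. Both are answered by a change over time within one group. Such a change mixes the quantity of interest with anything else that moved the proportion starting treatment over those 12 months. The design provides a second, randomised group measured over the same months, and even calls it the control, but the analysis leaves it out.

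At stake are the readings that the effect lasted and that the cheaper version works, and the cost per added contact built on the second of these.

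**Working it through.** **Timeline.** The planned windows are months 13-18 and 25-30. Cross-over Phase 1 takes three months (19-21). Then "There are 3 months between Phase 1 and Phase 2" (months 22-24): one for analysis, one for presenting findings, one for preparation and training. Phase 2 takes months 25-30. Training at former control clinics therefore falls in month 24 and the solutions follow.

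**Inputs from Sample size considerations.** Baseline 10%, 100 contacts per clinic per six months, ICC 0.05 to 0.10, alpha 0.05, 24 clinics. Assumed here: 12 clinics per group and a two-sided test. Not in the protocol, so also assumed: trend S between -5 and +10 points, and a between-period correlation of clinic effects (CAC) of 0.5 to 1.0.

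**1. Check of the inputs.** The protocol gives no power or effect figure for the cross-over. Its Table 2 reproduces with the usual two-proportion formula and design effect 1 + 99 × ICC: 0.053, 0.099, 0.141, 0.075, 0.131 and 0.182, against the stated 0.05, 0.10, 0.14, 0.08, 0.13 and 0.18.

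**2. What the planned comparisons estimate.** Let d be the loss of effect at the original intervention clinics and Es the streamlined effect, in percentage points. Original clinics show S - d. Former controls show S + Es.

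| S | d | Es | Original clinics | Former controls |
|---|---|---|---|---|
| 0 | 0 | 10 | 0 | +10 |
| +5 | 5 | 5 | 0 | +10 |
| +10 | 10 | 0 | 0 | +10 |
| -5 | 0 | 5 | -5 | 0 |

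The first three rows cannot be told apart. All would be read as a sustained effect and a working package; in the third, both readings are false. The fourth shows a lasting effect and a useful package both missed. A difference-in-differences on the same windows, (S + Es) - (S - d) = Es + d, removes S but gives +10 in all of the first three rows.

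**3. Chance of a spurious gain at former controls (Es = 0).** The variance of the mean change is 2 × p(1-p) × [(1-ICC)/100 + ICC × (1-CAC)]/12. For S = +5, the mean p is (0.10 + 0.15)/2 = 0.125, so p(1-p) = 0.1094. With ICC 0.05:

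- CAC 1.0: SE = √(0.2188 × 0.0095/12) = 0.0132. P = 1 - Φ(1.96 - 0.05/0.0132) = 0.97.
- CAC 0.5: SE = √(0.2188 × 0.0345/12) = 0.0251. P = 1 - Φ(1.96 - 0.05/0.0251) = 0.51.

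For S = +2 the range is 0.13 to 0.36. For S = +5 with ICC 0.10 it is 0.33 to 0.97.

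**4. Added contacts.** If "added" is counted before-after, as in the main study, then Es = 5 and S = +5 give 10 added starts per 100 contacts instead of 5, which halves the cost per added contact. With S = -5 there are none, and the ratio has no value.

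**5. What the concurrent data can give.** Let E be the effect in months 13-18, d1 and d2 the loss by months 19-23 and 25-30, and P any early effect of evaluation and discussion at former controls. The original-minus-former-control difference is:

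- months 19-23: E - d1 - P
- months 25-30: E - d2 - Es

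S cancels from both. The fall from the first to the second is Es + (d2 - d1) - P.

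**6. Precision.** At ICC 0.05, with former controls moving from 10% to 20% and original clinics steady at 20%, the difference-in-differences SE on the planned windows is 0.021 to 0.041, against 0.014 to 0.027 for before-after: about 1.5 times. For the months 19-23 contrast, five months at the planned rate give about 100 × 5/6 = 83 contacts per clinic and a design effect of 1 + 82 × 0.05 = 5.1. For 20% against 10%, SE = √[(0.16 + 0.09) × 5.1/(12 × 83)] = 0.036. The same formula with 100 contacts and design effect 5.95 gives 0.035.

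**The case against.** Several points on the other side stand.

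- **The protocol predicts no trend in treatment starts.** A reader might infer one from the remark that the rifampin trial is still running, "so findings from that RCT will not affect practise until close to the end of this study". That remark explains the choice of regimen, and the same paragraph says treatment initiation will not depend on the regimen. WHO promotion of LTBI treatment is described as already under way. A trend is possible and unmeasured; it is not forecast, and the sizes used above are assumptions.
- **Former controls are not untreated in months 19-23.** A reader might take those months as a clean randomised control period. The cross-over section counts evaluation and decision making as part of the intervention: staff and contacts are questioned in months 19-21, and solutions are discussed with clinic managers in month 23. It also notes that contacts can take several months to reach treatment, so some identified late in this window may start after training.
- **The final six months have no untreated group.** By then every clinic has had the intervention. Months 19-23 cover under half of the year that objective 3 names.
- **A between-group estimate of the streamlined effect has its own bias.** Later waning at the original clinics, d2 - d1, is added to it. In-service visits are scheduled only for the new intervention clinics, so stability cannot be presumed.
- **Model terms may be left to the SAP.** That is so for period terms. The comparisons themselves, however, are fixed in the protocol.

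These points limit what a fix can deliver. They do not make the before-after contrasts controlled.

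**Conclusion.** The point holds in this form: both effect comparisons in the cross-over are uncontrolled, and each is wrong by the full amount of any common trend, in either direction. The size cannot be stated, because the protocol gives no trend; a +5-point trend would equal half of the 10-point difference detectable at 10% baseline and ICC 0.05.

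It would go too far to say that objectives 3 and 4 cannot be answered. Costs can be measured regardless, and the plan still describes whether starts stay at the level reached. It would also be wrong to say that any trend flatters the intervention, since a falling one works against it. The randomised 18-month comparison is untouched. What is affected is the causal reading of the two cross-over comparisons and the added-contact denominator.

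The illustrative probabilities rest on 12 clinics per group, 100 contacts per clinic and window, and the assumed S and CAC.

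**What to change.** Amend the cross-over Data Analysis section as follows.

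1. Add the randomised difference, original intervention minus former control clinics, for about months 19-23, before training and solutions reach the former controls. Present it as an estimate of early persistence that is free of a common trend. State that it covers under half of the one-year objective, and that it is likely conservative because former controls are already in Phase 1 and transition.
2. Analyse all clinics and periods jointly in the same GEE, with period and group-by-period terms. Report the change in the between-group difference from months 19-23 to months 25-30 as a supportive estimate of the streamlined effect. State that it assumes no further waning at the original clinics after month 23, and that any waning is added to the estimate.
3. Keep the two planned comparisons, labelled as uncontrolled changes that cannot separate time trend from persistence or benefit.
4. Name the comparator for an added contact in the streamlined cost-effectiveness analysis.

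This changes wording and analysis only; the monthly outcomes are already to be collected. The price is wider intervals for the supportive streamlined estimate (about 1.5 times the before-after SE in the planned-window illustration) and assumptions that must be stated openly.

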### **Study design:**

We propose a cluster randomized trial at 36 sites in 6 countries. Sites randomized to the intervention group will receive a complex two-phase intervention lasting 18 months. Control sites will receive a stream-lined version of this 2-phase intervention after 18 months, while outcomes are continued to be measured at all sites for an added 12 months.

**Randomization** will be stratified by country, and restricted to ensure equal number of participants receiving or not receiving the intervention within each country. Following randomization, **in Phase 1**, a standardized public health evaluation will be conducted at all intervention sites to identify barriers to LTBI diagnosis and treatment initiation, in order to select the solutions to be used in Phase 2. This will include measurement of the key study outcomes (see below). To ensure standardization of data gathering we will use (i) current indicators of the LTBI cascade of care in the participating units (number of contacts per index case registered, investigated, started on treatment and completing treatment) and (ii) interviewer-administered standardized questionnaires – for patients with newly diagnosed active pulmonary TB, household contacts of these patients, clinic staff and administrators. These questionnaires will assess management of contacts, LTBI diagnosis and therapy, as well as TB-related knowledge, attitudes and beliefs from the perspective of these different participants. Results from this phase will be analysed, and used by the investigators, together with local public health officials, to decide on appropriate corrective solutions. In control sites we will gather data on study outcomes only (see below).

**In Phase 2**, solutions will be selected, and implemented at the intervention sites. Preparations and training of staff at each site will be conducted before the intervention begins, as soon as each site (clinic) is judged ready to begin. Study outcomes will continue to be measured at all sites through-out Phase 2.

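### Cross-over before-after comparison at former control sites: seen and investigated have no matched baseline, and completing has no fixed cohort or data cut-off

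*Protocol*

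**What the plan says.** The Data Analysis section of the cross-over study gives, as its second comparison, that "we will assess the increase in contacts seen, investigated, started and completing LTBI treatment at the former control sites". The stated method is a contrast of two six-month windows at those clinics, namely the closing half-year of the main trial and that of the cross-over.

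The cross-over Design section says that evaluation, transition and implementation together "should take a total of 12 months". Within that, "Phase 1 is shortened to 3 months", three months of transition follow, and "Phase 2 will last 6 months". The main Study design section describes the stream-lined package being given to control sites after month 18 "while outcomes are continued to be measured at all sites for an added 12 months".

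On data at control sites during the main trial, Study design states: "In control sites we will gather data on study outcomes only (see below". The Study Outcomes section lists the monthly items for all facilities: index cases, household contacts identified, and contacts starting treatment. Completion is to be collected later and retrospectively, from clinic records (Study Outcomes; Ascertainment of study outcomes). The Cascade indicators section covers intervention facilities.

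On regimen length, Rationale for study design says "The current standard in most countries remains INH for 6 or 9 months". The section on activities at control sites gives six months of INH as usual, and the Montreal and Calgary site descriptions say that therapy is individualized.

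**The concern.** The second comparison is a before-after contrast at the same clinics, so each measure must exist in both windows and be obtained in the same way. Four measures are named, but only starting treatment is clearly recorded monthly in both.

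Seen and investigated are intermediate cascade steps that control sites are not asked to record in the baseline window. The tool that would record them later, the Contact Management Registry, was kept out of control sites because the protocol regards it as part of the intervention. A before-after difference in these steps could therefore mix real change with more complete recording.

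Completion follows starting by the length of the regimen, which is at least as long as the six-month window under 6 or 9 months of INH. Whether the number refers to completions dated in the window, or to completions among those who started in it, decides which contacts are being measured. The sentence does not say.

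At stake is part of secondary objective 4, the impact of the streamlined package. A later analysis plan could define terms, but it could not supply baseline cascade data or late completion data that nobody had collected.

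**Working it through.** **Timeline.** 3 (Phase 1) + 3 (transition) + 6 (Phase 2) = 12 months, which reproduces the stated total. Counting on from month 18: Phase 1 is months 19-21, transition months 22-24, Phase 2 months 25-30. The after window is therefore exactly the six months in which the package is delivered. The baseline window is months 13-18.

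**What exists at former control sites**

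| Measure | Months 13-18 | Months 25-30 |
|---|---|---|
| Started | monthly count | monthly count |
| Seen, investigated | no monthly record | new registries, interim cascade analysis |
| Completing | retrospective, clinic records | retrospective, no cut-off stated |

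**Reach of the cross-over cascade review.** It takes about 100 contacts per site (about 30-50 index cases), the newest index case having been diagnosed six months before the review.
- Review at the start of Phase 1 (end of month 18): 18 - 6 = 12, so 0 of the 6 baseline months are covered.
- Review at the end of Phase 1 (end of month 21): 21 - 6 = 15, so at most 3 of the 6 (months 13-15). Months 16-18 are never covered.
- At the minimum volume of 40 index cases a year (3.33 a month), 30 cases span 30/3.33 = 9 months and 50 cases span 15 months. The latest review then has 3/9 = 33% or 3/15 = 20% of its span inside the baseline window. With 4.2 contacts per case, 100 contacts need 23.8 cases, or 7.1 months, giving 3/7.1 = 42%.
- At 250 cases a year (Benin's 500 in Table 1, assumed evenly split over two units), 30 cases span 30/20.8 = 1.4 months, all inside the window but only 1.4 of its 6 months.

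**Completion counted by date.** Start month = completion month minus regimen length D.
- D = 6: completions in months 25-30 come from starts in months 19-24.
- D = 9: they come from starts in months 16-21.
- The share of contacts starting evenly over the window who can finish inside it is max(0, 6 - D)/6: 0 for D = 6 and for D = 9. For an assumed 4-month regimen, possible where therapy is individualized, it is 2/6 = 33% at most.

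**Completion counted among starters.** Last completion = end of window + D.
- Starts in months 13-18: 18 + 6 = month 24, or 18 + 9 = month 27, both before month 30.
- Starts in months 25-30: 30 + 6 = month 36, or 30 + 9 = month 39, which is 6 to 9 months beyond the measurement period described in Study design.

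**The case against.** The best defence concerns completion. Secondary objective 1 defines it as a proportion of those who start. Study Outcomes and Ascertainment say that it occurs later and is gathered retrospectively, and the cross-over carries outcome measurement over from the main trial. The main trial has the same structure: starts in months 13-18 complete after its window closes. Nothing says that retrospective abstraction must stop at month 30. This stands, and it rules out two stronger conclusions that a reader might draw.

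- A reader might infer that almost no contact exposed to the package could be counted as completing. That follows only if completions are counted by date in the window, and the protocol's own definition points to the start cohort.
- A reader might infer that the completion comparison must show no effect whatever the package does. Even counted by date, this goes too far. Contacts who started six months of INH in months 19-24 are still on treatment for part of Phase 2, when in-service visits run. The protocol makes completion a focus of training if it falls below 50%, and it lists payment per medication renewal visit among possible incentives.

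On seen and investigated, the defence notes that the cross-over review does give a pre-package sample at each former control site. That also stands: there are some baseline data. They do not fill the window the comparison names, and their source may differ from that of the later data.

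Finally, a cut-off date could be left to an analysis plan. Whether records are abstracted after month 30, and whether a matched baseline review is done, are data-collection decisions and could not be.

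**Conclusion.** The point holds in a limited form. For seen and investigated, the stated comparison has no matched baseline: there is no routine record at control sites in months 13-18, and the retrospective sample reaches 0 to 3 of those 6 months. If the after figures come from the new registries, part of any increase may be a recording effect. The protocol gives no figure for how large that effect could be.

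For completing, the defect is an unfixed cohort and cut-off. Read as a dated count, it measures treatment begun before Phase 2. Read with the protocol's definition among starters, it works but needs records to about month 36 (6-month INH) or month 39 (9-month INH), against measurement described to month 30.

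This rests on the cross-over keeping its 3 + 3 + 6 month schedule and on 6 or 9 months of INH being the main regimens.

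A reader might infer that secondary objective 4 cannot be answered. The documents do not support that: starts and contacts identified are measured monthly at every site, and the cross-over cost-effectiveness measure is per added contact who starts treatment. The comparison of starts, that cost-effectiveness measure and the primary outcome are unaffected.

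**What to change.** 1. Restrict the monthly-count comparison at former control sites to contacts identified and contacts started.
2. Take seen and investigated only from cascade reviews that use the same record sources, abstraction method and lag before and after, with index cases from months 13-18 included in the baseline. With the existing six-month lag, the baseline review would be possible from 18 + 6 = month 24, and a review of index cases through month 30 from 30 + 6 = month 36. Otherwise drop these two measures.
3. State completion as the proportion completing among contacts who started in months 13-18 versus months 25-30. Give both cohorts equal follow-up from start, record the regimen, and schedule retrospective abstraction late enough for the regimens used (about month 36-39). Otherwise delete completing from this comparison. One limit remains: contacts who start a 9-month course in months 16-18 finish in months 25-27, so their treatment overlaps the package slightly.

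The cost is one later record abstraction and one matched cascade review per former control clinic, with this secondary result delayed by 6 to 9 months; the alternative is the loss of a secondary endpoint. Nothing changes for patients.
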